[REDACTED], and staff-assessed conjunctival redness will be recorded at approximately post second dose [REDACTED].

Post-EEC exit (approximately t = 215 minutes):

1) Subject assessed ocular itching and tearing will continue [REDACTED];

2) Staff assessed conjunctival redness will continue to be recorded post-EEC exit [REDACTED].

Subjects will be asked to return in 2 weeks (\pm 3 days) for Visit 4.

At Treatment EEC Session Two (Visit 4), all procedures performed at Visit 3 will be repeated except that each subject will be given a different treatment depending on the treatment sequence the subject was randomized to [Reproxalap Ophthalmic Solution (0.25%) (Treatment A), Reproxalap Ophthalmic Solution (0.5%) (Treatment B), or Vehicle Ophthalmic Solution (Treatment C)].

At the end of the EEC session, subjects will be asked to return in approximately two weeks (\pm 3 days) for Visit 5.

At Treatment EEC Session Three (Visit 5), all procedures performed at Visit 4 will be repeated except that each subject will be given a different treatment depending on the treatment sequence the subject was randomized to [Reproxalap Ophthalmic Solution (0.25%) (Treatment A), Reproxalap Ophthalmic Solution (0.5%) (Treatment B), or Vehicle Ophthalmic Solution (Treatment C)]. At the end of the visit, a urine pregnancy test will be administered to WOCBP.

Subjects will undergo ophthalmic examinations (Snellen VA, SLE, NCT, and a dilated fundus examination), clinical safety labs and vital signs will be collected to ensure safety prior to exit of the clinical trial.

Criteria for Inclusion:

Each subject must:

- Be at least 18 years of age at the time of screening of either sex or any race;
- Provide written informed consent;
- Be willing and able to follow instructions, and can attend all required clinical trial visits;
- Have at least a two-year history of moderate-to-severe ragweed-induced allergic conjunctivitis based on principal investigator's judgement;
- Have a positive skin prick test to ragweed pollen within the past year of the Medical Screening Visit (Visit 1);

[REDACTED]
[REDACTED]

- Confirmed absence of pregnancy according to a negative urine pregnancy test at the Medical Screening Visit (Visit 1);

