pemphigoid, significant conjunctival scarring, chemical burn, herpetic or neurotrophic keratitis, Cryopyrin Associated Periodic Syndrome (CAPS), or keratoconus;

[REDACTED]

[REDACTED]

Statistical Analysis:

Approximately 150 subjects with ragweed-induced, moderate-to-severe allergic conjunctivitis will be screened in the EEC in order to randomize approximately 75 subjects, and for 60 subjects to complete the study. Approximately twenty-five (25) subjects will be assigned to each of three (3) treatment sequences, ABC, BCA, and CAB. While not based on formal power considerations, 60 subjects completed is sufficient to produce reasonably reliable statistical conclusions based on the following:

[REDACTED]

Prior to database lock, the Sponsor will finalize a statistical analysis plan (SAP) that will detail all planned analyses. Any analyses conducted in addition to those specified in the SAP will be clearly documented as post hoc.

In brief, the efficacy analyses of all efficacy endpoints will be carried out in the Intent-to-Treat (ITT) population. Supportive analyses may also be provided for Itching endpoint(s) using the Per-Protocol (PP) population.

Descriptive statistics of all activity endpoints as well individual data listings will be presented by treatment group and efficacy measures. For each efficacy endpoints, treatment comparisons will be made between Reproxalap Ophthalmic Solutions (0.25% and 0.5%) and vehicle. The treatment comparison will be performed using a mixed-effects Analysis of Covariance Model (ANCOVA) for a crossover study for 3 periods.

[REDACTED]

The endpoints that will be analyzed are the following:

AUC 0-212 mins for Itching on VAS scale
AUC 0-212 mins for Itching on 9 points scale
AUC 0-210 mins for Conjunctival Redness on 9 points scale
AUC 0-212 mins for Tearing on 4 points scale
AUC 0-212 mins for TOSS
AUC 0-92 mins for Itching on VAS scale
AUC 92-212 mins for Itching on VAS scale
AUC 0-32 mins for Itching assessed by VAS Scale
AUC 32-72 mins for Itching assessed by VAS Scale
All 0 time-point measurements will be pre-EEC entry/ baseline values. All the time-points are approximate values

Additional Exploratory Analyses

In addition, descriptive statistics including Change from Baseline (CFB) for each treatment and each post-EEC time-point may be derived and used as exploratory efficacy endpoints to evaluate the efficacy of Reproxalap Ophthalmic Solutions (0.25% and 0.5%). Other exploratory analyses may be added post-hoc.

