10.9 Accountability and Background Characteristics

10.9.1 Enrollment and Disposition

The number of subjects enrolled, by study population and investigative site, will be presented by treatment group. The primary reasons for discontinuation will be summarized by treatment and based on the safety population. The number and percentage of subjects with protocol deviations or subjects requiring rescue therapy leading to exclusion from the PP population will be presented by reason for exclusion, stratified by treatment. All deviations and rescued subjects will be listed.

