Adjustments for Multiplicity	24
Interim Analysis	25
General Considerations	25
Subject Populations and Disposition.....	25
Discontinuations	26
Protocol Deviations/Violations.....	26
Data Sets Analyzed	26
Demographic and Other Baseline Characteristics	26
Pre-ecr MEASUREMENT for Visit 3, 4 and 5	27
Medical History And Concomitant Diseases.....	27
Concomitant Medication	27
Study Drug Administration	28
Efficacy Analyses.....	28
Safety Analyses	30
Change to the Planned Analyses.....	33
Appendix 1: Calculations.....	34
Tables, Listings and Figures (TLFs)	34

	Sponsor: Aldeyra Therapeutics, Inc. Sponsor Protocol No. ALDNS2-203-D1
---	---

I. INTRODUCTION

The purpose of the statistical analysis plan (SAP) is to describe the planned analyses and reporting for protocol 18-MO-001:

“An Exploratory Clinical Trial Evaluating Reproxalap Ophthalmic Solutions (0.25% And 0.5%) In Subjects With Seasonal Allergic Conjunctivitis Using The Environmental Exposure Chamber (EEC)”

This SAP is being written with due consideration of the recommendations outlined in the most recent International Council on Harmonization (ICH) E9 Guideline entitled Guidance for Industry: Statistical Principles for Clinical Trials and the most recent ICH E3 Guideline, entitled Guidance for Industry: Structure and Content of Clinical Study Reports (CSR).

This SAP is a summative and definitive plan, based on the final protocol dated November 22, 2018 (Version FINAL 4.0).

The SAP includes details of data handling procedures and statistical methodology. The SAP also outlines the statistical programming specifications for the Tables, Listings and Graphs (TLGs). No interim analysis is planned for this study.

The final statistical analysis will proceed exactly according to the SAP approved by the sponsor as well as by Inflamax Research.

The statistical analysis methods presented in this document will supersede the statistical analysis methods in the clinical protocol. If additional analyses are required to supplement the planned analyses described in the SAP, they will be labeled as post-hoc and will be identified in the CSR.

Responsibilities

Inflamax Research will perform the statistical analyses described herein and is responsible for the production and quality control (QC) of tables, figures, and listings associated with the analyses other than the post hoc analyses.

II. STUDY DESIGN

OVERVIEW OF STUDY DESIGN AND DOSING REGIMEN

ADX-102-AC-011/18-MO0001 is a single center study.

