Data Collected Outside Study Schedule

Data collected at visits that occurred outside the time windows specified in the protocol will be included in the data listings but will not be included in the analyses.

Definition of Baseline

In general, baseline is defined as the last observed measurement prior to the first dose of study medication during Pre-EEC entry at visit (visit 3, visit 4 and visit 5). If patient has more than one non-missing measurement at different time point prior to the first dose, average of these assessment score will be taken to derive the baseline value. The baseline will be used in the change from baseline calculation for each treatment period.

	
Sponsor: Aldeyra Therapeutics, Inc. Sponsor Protocol No. ALDNS2-203-D1

--	---

Derived Variables

- Age is calculated in years after rounding down as follows:
Year of age = (Date [in days format] informed consent signed - Date [in days format] of birth) / 365.25.
- Efficacy assessments will be performed on both eyes. For conjunctival redness, assessments will be made in both temporal and nasal regions. For a symptom and at a specific EEC time point, from the multiple scores observed, the maximum score from both eyes and regions when applicable will represent the worst symptom score and thus will be used for the statistical analysis. This implies that all efficacy summary tables and treatments comparisons will use the maximum observed score at each ECC time points. The Listings of efficacy data however will provide all scores for the eyes and the regions as applicable.

The efficacy endpoints AUC will also be derived using the maximum score at each time point. Similarly, TOSS will be derived using the maximum score at each time point for the ocular itching, conjunctival redness and tearing symptoms.

- TOSS will be derived as the sum total of maximum score from ocular itching, conjunctival redness and tearing symptoms. However, the EEC time points for the ocular itching and tearing symptoms is different from the time points for the conjunctival redness. The scheduled time points for ocular itching will be used to represent the TOSS scheduled time points.

XII. STATISTICAL ANALYSES

MISSING DATA

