	
Sponsor: Aldeyra Therapeutics, Inc. Sponsor Protocol No. ALDNS2-203-D1

---	---

[figure not shown]
[figure not shown]
[figure not shown]
[figure not shown]
corresponding electronic CRF along with the reason the medication was taken.

Medications will be coded according to the WHO drug dictionary which includes the WHO Drug Preferred Name and the ATC Classification Level 2 and 4. Prior and concomitant medication data will be listed by subject.

STUDY DRUG ADMINISTRATION

The dosing dates, times during Treatment Visits 3 to 5 will be listed by subject and visit.

EFFICACY ANALYSES

Treatment Comparisons

Sponsor: Aldeyra Therapeutics, Inc.
Sponsor Protocol No. ALDNS2-203-D1

The following 3 contrasts will be evaluated for each primary endpoint:

- Reproxalap Ophthalmic Solution (0.50%) vs. Placebo
- Reproxalap Ophthalmic Solution (0.25%) vs. Placebo
- Reproxalap Ophthalmic Solution (0.50%) vs. Reproxalap Ophthalmic Solution (0.25%)

POST HOC ANALYSIS

1. Additional inferential analysis may be performed whereby additional covariates and other fixed factors may be used in models, depending on the significance of the term and the impact on contrast outcomes.
2. Responder analyses may be performed whereby treatment response may be defined as one and two-point improvements from mean and within-subject baseline and peak scores. In addition to GEE, time to event analyses may also be performed.

[REDACTED]	Sponsor: Aldeyra Therapeutics, Inc. Sponsor Protocol No. ALDNS2-203-D1
------------	---

[REDACTED]

[REDACTED]

[REDACTED]

[REDACTED]

[REDACTED]

SAFETY ANALYSES

All safety data will be analyzed using Safety population.

For safety analysis, summary descriptive statistics such as N, mean, SD, median, minimum and maximum will be provided by treatment group for continuous variables. Frequency distribution as number of subjects and percentage of subjects will be provided for categorical variables. No formal inferential tests will be performed on safety data.

Adverse Events/Adverse Drug Reactions

AEs will be coded using the Medical Dictionary for Regulatory Activities (MedDRA) coding dictionary [REDACTED] preferred term (PT) and system organ classification (SOC). Subjects will multiple events within the same SOC and/or PT are only counted once within the respective frequencies.

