	
Sponsor: Aldeyra Therapeutics, Inc. Sponsor Protocol No. ALDNS2-203-D1

--	---

- Summary of TEAEs categorized by death, serious AEs, leading to withdrawal and related to study drug (safety/ocular/non-ocular)
- Summary of TEAEs by system organ class and MedDRA preferred term (safety/ocular/non-ocular)
- Summary of TEAEs by severity (safety)
- Summary of TEAEs by relation to study drug (safety)

Adverse events will be listed as:

- Adverse events by subject and AE number
- Adverse events that caused the subject to discontinue
- Serious AEs

Severity.

Severity is classified as mild, moderate or severe. Missing severity for TEAEs will be counted as severe.

Adverse events with a missing relationship to study medication will be noted as “related” to study medication. If a patient reports the same AE more than once within the same SOC/PT, the AE with the strongest relationship to study medication will be used in the relationship summaries.

Pregnancies

Urine pregnancy tests will be performed from Screening Visit 1 through final treatment Visit 5. Pregnancy test results will be listed by subject and visit.

Vital signs

Blood pressure (systolic and diastolic, mm Hg), pulse rate (beats/min), respiratory rate (breaths/min) and body temperature (degree Celsius) will be assessed from Screening Visit 1 to final treatment Visit 5. The vital signs at EEC Visit 5 will be assessed at pre and post EEC time points, whereas the vital signs at EEC Visit 3 and Visit 4 will only be made at pre EEC time point. All vital signs data will be listed by subject, visit and time point as applicable.

Fundus Assessment

Fundus assessment will be performed at Screening Visit 1 to final treatment Visit 5, and will be listed by subject, visit and eye.

	Sponsor: Aldeyra Therapeutics, Inc. Sponsor Protocol No. ALDNS2-203-D1
---	---

Intraocular Pressure Readings (IOP)

Non-contact tonometry (NCT) assessment will be performed at Screening Visit 1 and at Visit 3 to Visit 5 to measure the Intraocular Pressure (IOP). The collected data (average of 3 readings for each eye) will be listed by subject, treatment, visit and time point as applicable. Summary statistics of the average of 3 IOP readings for treatment Visit 3 to Visit 5 for each eye will be tabulated by treatments and time points and presented for both Right and Left eyes.

Visual Acuity (VA)

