VA assessment will be performed at each visit. Data will be listed by subject, visit, treatment, time point and eye as applicable. Summary statistics of Visual Acuity for treatment Visit 3 to Visit 5 will be tabulated by treatment and eye.

Slit lamp Assessment

[figure not shown]
Slit lamp assessment will be performed at each visit. Data will be listed by subject, visit, treatment, time point and eye as applicable. Abnormalities and clinically significant findings will also be listed.

CHANGE TO THE PLANNED ANALYSES

The final version of the protocol specified additional efficacy assessments for Post-EEC exit time points. However, the list of efficacy endpoints in the protocol do not cover the data related to these Post-EEC exit time points. Therefore, the following additional efficacy endpoints were added in the SAP.

- AUC 0-274 mins for Itching on VAS scale
- AUC 0-274 mins for Itching on 9 points scale
- AUC 0-270 mins for Conjunctival Redness on 9 points scale
- AUC 0-274 mins for TOSS

	
Sponsor: Aldeyra Therapeutics, Inc. Sponsor Protocol No. ALDNS2-203-D1

--	---

TABLES, LISTINGS AND FIGURES (TLFs)

The TLFs shells for this study is provided in a separate document SAP Mock TLFs. The shells may change due to unforeseen circumstances such as data formatting. These shells may not be reflective of every aspect of this study but are intended to show the general layout of the Tables, Listings and Figures that will be included in the final report. TLFs are numbered following the E3 "Structure and Content of Clinical Study Report".

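### The SAP leaves every out-of-window visit out of every analysis, so late dosed sessions and observed IOP and visual acuity readings are lost because of the visit date alone

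*SAP*

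**What the plan says.** The rule is in SAP Section XI, Data Collected Outside Study Schedule: data from visits "outside the time windows specified in the protocol will be included in the data listings but will not be included in the analyses". It names no exempt population, data type or direction of departure.

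The text around it reads as follows.

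- **Efficacy set.** The protocol synopsis says "the efficacy analyses of all efficacy endpoints will be carried out in the Intent-to-Treat (ITT) population".
- **Safety set.** SAP Safety Analyses: "All safety data will be analyzed using Safety population". For IOP, "Summary statistics of the average of 3 IOP readings for treatment Visit 3 to Visit 5 for each eye will be tabulated". For visual acuity, "Summary statistics of Visual Acuity for treatment Visit 3 to Visit 5 will be tabulated by treatment and eye". Both are listed as safety endpoints in SAP Section X.
- **Populations.** The ITT and Safety definitions in SAP Section IX carry no visit-window condition. The SAP's list of per-protocol exclusions covers only product not received as assigned and unmet eligibility criteria.
- **Deviations.** Protocol 10.9.1 says the number of subjects with "protocol deviations or subjects requiring rescue therapy leading to exclusion from the PP population will be presented by reason for exclusion".
- **Precedence.** SAP Introduction: "The statistical analysis methods presented in this document will supersede the statistical analysis methods in the clinical protocol".
- **Adverse events.** SAP Derived and Imputed Data assigns a treatment-emergent event to the last treatment given before onset, whatever the visit date.
- **Windows.** For Visit 4 the synopsis says "Subjects will be asked to return in 2 weeks", plus or minus 3 days. Protocol 3.1 and SAP Section II give a minimum of two weeks for Visit 4 with no tolerance. For Visit 5 they give the same minimum with a 3-day tolerance either way.

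Table 1 is not shown, and SAP General Considerations and parts of Efficacy Analyses are redacted.

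**The concern.** The rule works on records and applies equally to the ITT, completer and per-protocol analyses. It treats two different departures alike. A session held too early may carry residual drug effect or incomplete mast cell recovery, so leaving it out has a scientific reason. A session held late has had a longer washout than planned, so the washout rationale gives no ground for discarding its efficacy scores. Neither departure is a reason to leave an IOP or visual acuity reading, taken after randomised product was instilled, out of a descriptive safety table.

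At stake are some precision in the treatment contrasts and some observed safety data, in a trial whose stated objectives include safety and tolerability.

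**Working it through.** The plan states no figure for this point, so there is nothing of its own to reproduce. The check has three steps.

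**1. Does any visible text lift the rule?** The ITT and Safety definitions select subjects and say nothing about visit timing. The safety section names the population but does not waive the rule. The missing-data rule does not mention timing exclusions. The precedence statement in the SAP Introduction means the protocol's ITT statement cannot be relied on to override the rule. No visible exception was found. Adverse event tables fall outside it because they depend on onset, not on a visit.

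**2. What would dropping sessions cost?** Inputs from the documents: sequences ABC, BCA and CAB, three periods, 25 subjects per sequence (75 in all), hence 2 x 75 = 150 Visit 4 and Visit 5 sessions. Assumed, because the documents give no value: 5% or 10% of those sessions out of window, within-subject correlation 0.3 to 0.85, and sessions dropped at random and not imputed. The model has a random subject effect with fixed period and treatment effects. The result is the generalised least squares variance of the active-vehicle contrasts, averaged over random removal patterns and divided by the variance with no removals. The rise in standard error is the square root of that ratio minus 1. The equivalent number of subjects lost is 75 x (1 - 1/ratio).

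| Sessions dropped | Variance ratio (correlation 0.3 to 0.85) | Rise in SE | Equivalent subjects lost |
|---|---|---|---|
| 8 (5%) | 1.046 to 1.057 | 2.3% to 2.8% | 75 x (1 - 1/1.046) = 3.3 to 75 x (1 - 1/1.057) = 4.0 |
| 15 (10%) | 1.091 to 1.110 | 4.4% to 5.4% | 75 x (1 - 1/1.091) = 6.3 to 75 x (1 - 1/1.110) = 7.4 |

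Adding a session-level baseline covariate leaves these ranges essentially unchanged. With 60 subjects the rises are 2.2% to 2.6% and 4.4% to 5.4%. The removals mix early and late sessions. Because the rise is close to proportional to the number dropped, if half were late, roughly half of it would be recoverable.

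For IOP and visual acuity, balanced losses would leave 75 - 8/3 = about 72, or 75 - 15/3 = 70, of 75 sessions in each treatment's summary.

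**3. Should short-washout sessions go back into the main analysis?** In these sequences, vehicle at Visit 4 or 5 always follows 0.5%, and 0.25% always follows vehicle. Suppose a share f of Visit 4 and 5 sessions carries a fraction L of the preceding treatment's effect. Two of the three periods are exposed, so the 0.25%-vehicle contrast is pulled toward zero by (2/3) x f x L x (effect of 0.5%). With f of 5% to 10% and L of 25% to 50% (both assumed):

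- equal effects: 0.667 x 0.05 x 0.25 = 0.8% to 0.667 x 0.10 x 0.50 = 3.3%;
- 0.5% twice as effective as 0.25%: 1.333 x f x L = 1.7% to 6.7%.

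That is a reason to keep excluding early sessions from the main efficacy analysis.

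**The case against.** The strongest reply has four parts.

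- **Hidden text.** The rule defers to protocol windows, whose natural home is Table 1, and an exception could sit in the redacted General Considerations. This stands as a limit. If an exception exists, a cross-reference is enough.
- **Perhaps no Visit 4 session can be late.** Protocol 3.1 and the SAP set only a minimum for Visit 4. On that wording the efficacy loss arises only at Visit 5, or under the synopsis tolerance or a Table 1 limit. This narrows the efficacy part but does not touch IOP and visual acuity, which are lost from early sessions as well.
- **A timing exclusion is legitimate in a washout design.** Agreed for short washouts. It does not extend to late sessions or to safety readings.
- **The effect is hypothetical and small.** No rate is given, and zero is compatible with the documents. The readings stay in the listings, safety data receive no inferential tests, and adverse event incidence, the primary safety variable, is unaffected. All true, and the reason this is minor.

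A reader might also infer more than the documents support.

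- *That subjects leave the ITT or Safety population.* They do not. The definitions select subjects, while the rule selects records.
- *That protocol 10.9.1 is contradicted.* It reports per-protocol exclusions and does not say timing departures are handled only there.
- *That the rule biases the comparison or inflates type I error.* Nothing shows that visit timing depends on treatment or response, and the trial has no formal hypotheses.
- *That the differing return wording makes the rule unworkable.* For Visit 4, days 11 to 13 and day 18 onward do classify differently under the synopsis and under Section 3.1. But Table 1 is not visible, and other text points to about 14 days: the approximate two-week washout, and 8 + 2 + 2 + 2 = 14 weeks, the duration in protocol 3.5. This is an alignment note only.

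**Conclusion.** The point holds as a minor one. On the visible text, the rule removes late dosed sessions from the ITT efficacy comparison and removes observed IOP and visual acuity readings from the treatment summaries, with no stated reason beyond the visit date. Leaving short-washout sessions out of the main efficacy analysis is defensible and is not criticised here.

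The rise in standard error of about 2% to 5% is an illustration. It rests on an assumed 5% to 10% out-of-window rate at Visits 4 and 5, random removal and no imputation, and it overstates what can be recovered, because some of those sessions would be early. The SAP does not say whether excluded data would count as missing. If they did and were filled with treatment-by-visit means, the reported standard error would be too small rather than larger. Confidence is medium because Table 1 and General Considerations cannot be read.

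**What to change.** Replace the sentence in SAP Section XI with:

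*Observed safety data from every session in which IP was given are included in the Safety analyses. Efficacy data from dosed sessions later than the visit window are included in the ITT analysis under the nominal visit and excluded from PP. Sessions with a washout shorter than the protocol minimum are excluded from the main efficacy analysis and included in one ITT sensitivity analysis. Data excluded for timing are not imputed under the missing-data rule.*

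Add late sessions to the per-protocol exclusions in SAP Section IX so that the two sections agree. As a housekeeping step before unmasking, align the synopsis, protocol 3.1 and SAP Section II with the Table 1 window if it has one. The lower limit matters most, since it still decides which sessions enter the main efficacy analysis.

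The cost is a few lines of SAP text, one sensitivity table and slightly more variable washout times in ITT. No extra data or subjects are needed.
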